Official Title: Optimizing Dementia Care through Collaborative Recovery Interventions

NCT: NCT02585232

1. **Principal Investigator:** [name]
2. **All co-investigators:** [name]; [name], MA; [name], MS; [name]; [name], MEd; [name], MA; [name], BA; [name], [name], BS
3. **Consultants:** [name]; [name]; [name]; [name]
4. **Sponsor of the study or funding agency (if applicable):** VA Rehabilitation Research & Development Service (Rehab R&D) (D1824-W; Application Number: 1IK2RX001824-01A1)

5. Research setting:

This is a community-based study. All in-person study procedures will occur in a convenient community-based setting of the participant's choosing (e.g., their home, a local library, a community center, TVAMC campus, etc.). Most interactions (intervention & assessment) will occur over the telephone.

6. Purpose of the study (including hypothesis to be tested):

The purpose of this randomized controlled pilot study is to examine the preliminary effectiveness, feasibility, and potential treatment moderators (e.g., behavioral symptoms and spousal relationship status) of a newly developed intervention that combines elements of the established care consultation (CC) approach with additional counseling modules (CC+C).

Our specific aims and hypotheses follow:

Aim 1: Manualize the integration of care consultation and counseling components. The study team will begin this five-year study by refining and operationalizing the CC+C intervention. The CC+C intervention is guided by a rehabilitation and recovery-based conceptual model to address the most common high distress situations (e.g., relationship distress, veteran or caregiver depression, anxiety, or pain).

Aim 2: Evaluate preliminary effectiveness and feasibility of the CC+C Intervention. A randomized controlled pilot study of distressed dyads will be completed to compare: 1) the established CC intervention, to 2) the CC+C intervention on veteran and caregiver outcomes at 6 months.

Aim 3: Conduct exploratory analyses of the CC+C intervention on veteran long-term care placement at 6 and 12 months and examine two key treatment moderators

(behavioral symptoms and spousal relationship status) that may impact intervention engagement and response to treatment.

Hypotheses for Aims 2 and 3:

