Participants assigned to both groups will have: 1) reduced unmet needs, 2) reduced depressive symptoms, and 3) higher levels of satisfaction with care at 6 months than their baseline assessment values.

Caregivers assigned to CC+C will have greater reductions in caregiver burden at 6 months than those assigned to CC alone. Indicators of relationship strain (e.g., marital distress and/or mutuality) will show greater improvement in CC+C than CC at 6 months. 6 month gains in shared pleasant events, social engagement, and quality of life will also be greater in CC+C than in CC alone. 6-month desire to institutionalize will be lower in the CC+C group than those randomized to CC. Treatment engagement (e.g. action plan completion, attendance) is also predicted to be higher in the CC+C group than in CC.

For Aim 3, we anticipate that individuals who receive the CC+C intervention will have lower rates of placement in long-term care facilities at 6 and 12 months than those who receive CC alone. We also expect that behavioral problems will impact treatment outcomes such that those dyads with higher levels of behavioral disturbance at baseline will have greater change scores at 6 months. Spousal relationship to the veteran is also expected to moderate treatment outcome such that spousal caregivers are anticipated to have lower change scores compared to non-spousal caregivers across time; however, we expect this effect to be attenuated in the CC+C condition.

7. Background, including results of relevant research, gaps in the current knowledge.

Scope of the Problem

Over five million Americans are diagnosed with Alzheimer's disease or a related disorder (ADRD) and rates are expected to triple by 2050¹. It is the 6th leading cause of death in the United States and one in three older adults will have dementia when they die².

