Missing values are unavoidable in applied clinical intervention research. Where possible, variables to index the number and reasons for missing values will be documented. Based on the distribution of these missing value indices we may choose to eliminate some participants from the analyses ("list-wise deletion"). The extent that missing values are related to the independent (treatment group) or outcome variables will be assessed and if necessary controlled for statistically. Individuals who complete at least four sessions of the intervention (CC or CC+C) will be included in final analyses when time 2 data are available. Strict intention-to-treat methodologies are too conservative for this relatively small initial pilot study.

Data Analysis:

A series of one-way between subjects analyses of covariance (ANCOVAs) will be used to examine the main effect of “group” on 6 month variables of interest while controlling for values at baseline. The dependent variable in these analyses will be change scores with pre-treatment scores as the covariate. This analysis is statistically equivalent to ANCOVA with pre-treatment scores as the covariate and 6-month scores as the dependent variable, but it has an interpretational advantage in that the change scores represent an individual treatment effect (change during treatment). The change scores also represent the interaction term of a 2 (Group) X 2 (Time) repeated measures ANOVA. Consequently, when other covariates are added to the ANCOVAs to address treatment moderation effects, those covariate effects will be directly interpretable as moderator effects. That is, the added terms will assess the effects of the covariates on changes during treatment irrespective of Group (essentially a Time by Covariate interaction). When the interaction (multiplicative product) of covariate and Group is also added as another term in the ANCOVA, that interaction term will supply the moderating effect of the covariate on change during treatment as function of Group (i.e., differential effect of treatment as a function of the covariate).

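### The analysis plan calls a covariate effect pooled over both arms a moderator effect; it identifies predictors of change, and only the Group-by-covariate term can show moderation of CC+C versus CC

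*Combined protocol and SAP*

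**What the plan says.** Section 6 (Purpose) sets out to examine "potential treatment moderators (e.g., behavioral symptoms and spousal relationship status) of a newly developed intervention", meaning CC+C. Aim 3 repeats that the study will "examine two key treatment moderators" and adds that they may affect engagement and treatment response.

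The Aim 3 hypotheses in the same section differ in form:

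- Behavioural symptoms: "those dyads with higher levels of behavioral disturbance at baseline will have greater change scores at 6 months". No arm is mentioned.
- Spousal status, first half: "spousal caregivers are anticipated to have lower change scores compared to non-spousal caregivers across time". Again no arm is mentioned.
- Spousal status, second half: "we expect this effect to be attenuated in the CC+C condition". This is a contrast between arms.

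Section 20 (Data Analysis) specifies ANCOVAs of 6-month change on Group with the baseline score as covariate. For moderation, further covariates are added, and "those covariate effects will be directly interpretable as moderator effects". The text then explains that "the added terms will assess the effects of the covariates on changes during treatment irrespective of Group". The next sentence begins "When the interaction (multiplicative product) of covariate and Group is also added as another term in the ANCOVA" and correctly identifies that product as the differential treatment effect.

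**The concern.** One label covers two different quantities. A covariate effect that is the same in both arms says who changes more. It does not say for whom CC+C does better than CC. Section 16 confirms that every participant receives an active intervention, so there is no untreated arm against which the pooled effect could be read as response to treatment. It may equally reflect natural course, regression to the mean or general prognosis.

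The exposure is greatest for behavioural symptoms, because that hypothesis can be met by the pooled term alone and section 6 calls the variable a treatment moderator. A reader could then conclude that CC+C should be aimed at dyads with more behavioural disturbance, when the data had shown only that such dyads change more under either intervention. Section 32 says that the results will serve as pilot data for future grant proposals, so the label could carry into the design of a later trial.

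**Working it through.** **No figure to reproduce.** The documents give no alpha, power, effect size or SD for any analysis; section 20 refers to grant text for the power calculation. The only usable figure is the target of 50 completers at 6 months. The point itself is algebraic and textual; the numbers below only illustrate it.

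**Step 1: what each term estimates.** Let G = 0 for CC and 1 for CC+C, and let X be the covariate.

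- Pooled model: change = a + b·baseline + g·G + c·X. The CC+C minus CC difference at any X is g. It does not depend on X, whatever the value of c. So c carries no information on moderation of the arm contrast.
- With the product: change = a + b·baseline + g·G + c·X + d·G·X. The difference at X is g + d·X. Moderation is d.

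**Step 2: match terms to hypotheses.**

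| Hypothesis (section 6) | Term that tests it | Type |
|---|---|---|
| More behavioural disturbance, greater change | c | predictor |
| Spouses show lower change | c | predictor |
| Spousal effect attenuated in CC+C | d | moderation |

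Only the third row concerns moderation of CC+C versus CC, yet section 20 attaches the moderator label to c.

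**Step 3: how often the two terms would disagree.** Assumptions: 25 per arm (allocation ratio not stated), standard normal covariate, d = 0, two-sided 5%, partial correlation r of X with change as listed. Simulation, 10,000 trials per setting:

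| r | pooled term p<0.05 | product term p<0.05 | pooled significant, product not |
|---|---|---|---|
| 0.2 | 28% | 5% | 27% |
| 0.3 | 56% | 5% | 53% |
| 0.4 | 82% | 5% | 79% |

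Check by noncentral F with 1 and 46 df and noncentrality 50·r²/(1−r²). At r = 0.2 this is 50 × 0.04/0.96 = 2.08, giving power 29%. At r = 0.1 it is 50 × 0.01/0.99 = 0.51, giving 11%. The pooled figure therefore depends strongly on the assumed r; the product-term figure does not.

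**Step 4: precision of the product term at 50 completers.** For a continuous covariate, the standard error of the difference in slopes is about √(1/24 + 1/24) = 0.289 residual SD per covariate SD. Times t(0.975; 45 df) = 2.014, the half-width is 0.58; the simulated median is 0.60.

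For spouse versus non-spouse, let s be the assumed share of spouses. The half-width is about 2.014 × √(2·[1/(25s) + 1/(25(1−s))]):

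- s = 0.5: 2.014 × 0.566 = 1.14 (simulated 1.17).
- s = 0.8: 2.014 × 0.707 = 1.42 (simulated 1.49).

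**Step 5: a threshold of 0.01 on the product term.** Partial eta squared = F/(F + 45), so 0.01 corresponds to F = 45 × 0.01/0.99 = 0.455. With d = 0, P(F(1,45) > 0.455) = 0.504. A null product term passes about half the time.

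**The case against.** The strongest reply is that section 20 hides nothing. It says at once that the pooled effect ignores Group, and it reserves the differential effect for the product. On this reading the authors treat change itself as the response, so a covariate that alters change moderates Time, and the complaint is about one word. Aim 3's broad reference to treatment response also fits, since both arms are treated. What stands is that the two quantities are openly defined. What does not stand is that the label is harmless: section 6 ties moderation to the new intervention, and with no untreated arm the pooled term cannot speak to that.

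Four stronger inferences might be drawn, and the documents do not support them.

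- *That the product term is left optional or omitted.* The conditional wording that introduces it also introduces the pooled step, so it cannot be read as optional for one and planned for the other. The spousal hypothesis cannot be tested without the product. For behavioural symptoms the text is simply not explicit.
- *That the behavioural-symptom hypothesis is tested with the wrong term.* As worded, it is a pooled prediction and the pooled term tests it correctly. Only calling the result moderation would be wrong.
- *That the percentages in the working are false-positive rates of the plan.* They are power to detect a real predictor under assumed correlations. No sentence says a significant pooled term will be reported as a difference between CC+C and CC.
- *That the plan judges moderators by the 0.01 cut-off.* Section 20 states that cut-off for between-groups effects and gives no rule for moderator terms.

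**Conclusion.** The point holds as a mislabelled estimand. The pooled covariate effect is a predictor of change across both arms; the Group-by-covariate term is the moderator effect. Following the text, a pooled behavioural-symptom effect could be reported as moderation of the new intervention without any evidence about the arm contrast.

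Severity is minor. Aim 3 is exploratory, the right term is already described, and the main group comparisons and the placement analyses are unaffected. The conclusion rests on the algebra and the wording. The correlations, the 5% level, equal allocation and the spouse share are assumptions that affect only the illustration.

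**What to change.** In section 20, Data Analysis:

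1. Call covariate main effects predictors of change across both arms.
2. State that the Group-by-covariate term will be fitted for both Aim 3 moderators.
3. State that moderation of CC+C versus CC is judged only from that term, reported as an estimate with a 95% CI.
4. If a partial eta squared threshold is ever applied to that term, do not use 0.01.

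In the section 6 hypotheses, label the behavioural-symptom hypothesis and the first half of the spousal hypothesis as predictor hypotheses. The investigators' question need not otherwise change.

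The cost is a few sentences and the fitting of a term already described; no new data are needed. The real downside is imprecision. With about 50 completers, a 95% CI half-width near 0.6 residual SD per covariate SD, and wider for spousal status, means that fewer moderator claims will be possible.

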Veterans have high rates of known risk factors that place them at increased risk of developing dementia including: PTSD,³ diabetes^{4,5}, substance use disorders,⁶ and cardiovascular disorders.⁷ Over 7% of veterans 65 and over receiving care through the Veteran's Health Administration (VHA) are currently diagnosed with dementia.⁸ In a study of dementia prevalence among VHA system users, [name], [name], and colleagues found that diagnosis by VISN varied between 5.8% to 9.4%.⁸ VISN 7, where the current work is proposed, had the highest dementia rates of any VISN in the country and was in the region with the greatest rates overall (i.e., the southeast) perhaps reflecting differences by race,⁹ educational achievement,¹⁰ rurality,¹¹ and/or cardiovascular morbidities.

Spouses comprise the largest group of caregivers for individuals with ADRD. This is particularly true for veterans with dementia, most of whom are men cared for by their

wives.¹² Decades of research suggests that spousal caregivers are uniquely vulnerable due to increased isolation, older age, and cohabitation status which reduce opportunities for respite.¹³ Couples in which one individual is diagnosed with dementia often experience substantial depression and frustration adjusting to functional changes and losses in roles, relationship, and independence of the declining loved one.¹⁴⁻¹⁶ Changes in shared intimacy, emotional support, companionship, and reciprocity are consequences of memory loss¹⁷ and associated cognitive changes resulting in grief reactions in up to 71% of caregivers.¹⁸ Some research has cited loss of the relationship with the person as the most distressing element of the disease for caregivers and directly predictive of depression above other aspects of the caregiving context.^{14,17} The unique functional and behavioral impairments associated with ADRD contribute substantially to psychological and physical morbidity of family caregivers and high rates of nursing home placement, with 60% of ADRD caregivers rating the emotional stress of caregiving as “high or very high,” and over one third reporting depressive symptoms.

Gaps in Current Knowledge

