- b. **Demographics** including: sex, age, primary racial or ethnic group, education, living arrangement, time since diagnosis, years married, number of marriages, number of children, and income adequacy will be collected for the veteran and their caregiver. Income adequacy will be assessed with a single item asking about difficulty paying for the basics, (1 = very difficult to 5 = not very difficult). Individuals will be asked if they have had any previous counseling experience, are taking any antidepressants, anxiolytics, or memory enhancers and whether doses have been stable for the past 3 months.
- c. **Health Literacy** will be measured using a 4-item screener to identify individuals with health literacy issues that could impact their ability to complete self-report measures.
57,58
- d. The **Montreal Cognitive Assessment (MoCA)**³⁵ a 30-point cognitive screening instrument with excellent discriminative power to detect mild cognitive deficits will be used to measure cognitive status.
- e. The **Physical Self-Maintenance (PSM) and Instrumental Activities of Daily Living (IADL) Scale**³⁶ will be used to assess functional status or independence in daily care needs across six physical care domains (i.e., activities of daily living, ADL) and eight IADL domains.
- f. The **Revised Memory and Behavior Problems Checklist (RMBPC)**³⁷ which provides an estimate of the frequency of problems and the impact that these problems have on the caregiver will be used to rate behavioral symptoms of dementia.
- g. The **Cornell Scale for Depression in Dementia (CSDD)**³⁸ which relies on an interview with the individual and the caregiver will be used to assess depressive and anxiety symptoms.

- h. The **Quality of Life in Alzheimer's Disease scale (QOL-AD)** will be used to assess quality of life.³⁹ Patients and caregivers rate thirteen domains: physical health, energy, mood, living situation, memory, family, marriage, friends, chores, fun, money, self and life as a whole, using a Likert-type scale.
- i. The **Euro-QoL-5 Domain (EQ-5D)** mobility, selfcare, and usual activities subscales will be used to assess autonomy and functional dependence.⁴⁰ Health-related quality of life is assessed for five domains: mobility, self-care, usual activities, pain/discomfort and anxiety/depression. Caregivers also complete this measure, as has been done in previous studies with individuals with mild to moderate dementia.^{40,41,42}

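### With the baseline score in the model, the pooled spousal-status and behavioral-symptom effects are differences at equal baseline, not the Time by Covariate interactions that Section 20 calls them

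*Combined protocol and SAP*

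**What the plan says.** Section 20, Data Analysis, sets out the model and its interpretation in four steps.

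- The model: "The dependent variable in these analyses will be change scores with pre-treatment scores as the covariate".
- Its equivalent form: "This analysis is statistically equivalent to ANCOVA with pre-treatment scores as the covariate and 6-month scores as the dependent variable".
- The link to repeated measures: "The change scores also represent the interaction term of a 2 (Group) X 2 (Time) repeated measures ANOVA".
- The inference drawn for covariates added to study moderation: "the added terms will assess the effects of the covariates on changes during treatment irrespective of Group (essentially a Time by Covariate interaction".

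The product of covariate and Group is a separate, further term, meant to capture differential response to treatment.

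Section 6 states two Aim 3 hypotheses that rest on the pooled covariate effect. For behavioral symptoms, "those dyads with higher levels of behavioral disturbance at baseline will have greater change scores at 6 months". For relationship status, "spousal caregivers are anticipated to have lower change scores compared to non-spousal caregivers across time", with the gap expected to shrink under CC+C. Nothing in Section 20 drops the baseline score for these tests or says that their results are conditional on it.

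**The concern.** The second and fourth steps conflict. If the model is the same whether the outcome is change or the 6-month score, a covariate coefficient cannot be specific to change. It is a comparison at 6 months between people with equal baseline scores. The repeated-measures reading in the third step belongs to a change-score model without the baseline covariate, which is not the model specified.

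For a randomized factor this matters little, because baseline is balanced in expectation. Spousal status and RMBPC are not randomized. The documents give reasons to expect both to track baseline outcomes. Section 7 says that "spousal caregivers are uniquely vulnerable due to increased isolation, older age, and cohabitation status", and Section 17 (Measures, item f) says that the RMBPC "provides an estimate of the frequency of problems and the impact that these problems have on the caregiver".

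At stake is a baseline difference that reappears as an effect on change. On a scale where higher is worse, if spouses start with more burden, the artefact shows them improving less. That is the direction Section 6 predicts, if a lower change score means less improvement. For RMBPC the same artefact makes higher symptoms look like worse change, against the stated hypothesis if change means improvement.

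**Working it through.** **Inputs from the documents.** The model and hypotheses above, and 50 completers at 6 months (Section 20, target sample size). The plan states no figure for this point, so there is nothing to reproduce. It also gives no alpha, correlation, reliability or SD.

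**Inputs assumed.** Two-sided 5% level; baseline gap between spouses and non-spouses d = 0.3 to 0.8 SD, with a 50/50 split; within-group correlation of baseline and 6-month score r = 0.5 to 0.9; for a continuous covariate, correlation 0.5 with the true outcome level and outcome reliability 0.6 to 0.8. In every setting the true scores do not change, and neither Group nor the covariate affects change.

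**Step 1: the algebra.** For a covariate Z, least squares gives

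Time × Z = c + b × g,

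where c is the baseline-adjusted coefficient of Z, b is the slope of change on baseline, and g is the baseline difference per unit of Z. The two agree only if b = 0 or g = 0.

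On one simulated data set of 50, c was 0.2127 with either change or the 6-month score as outcome, so the plan's equivalence statement is right. Time × Z in the same data was 0.1521. The difference, 0.1521 − 0.2127 = −0.0606, is b × g.

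**Step 2: size for spousal status.** With no true change, b = −(1 − r), g = d and Time × Z = 0. Hence c = (1 − r) × d.

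| r | d (SD) | c = (1 − r)d | False rejection, baseline-adjusted, n = 50 |
|---|---|---|---|
| 0.9 | 0.3 | 0.03 | about 5% to 6% |
| 0.7 | 0.5 | 0.15 | 10.5% |
| 0.7 | 0.8 | 0.24 | 18.6% |
| 0.5 | 0.8 | 0.40 | 27.5% to 30% (separate runs) |

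Change on Group and Z without the baseline score rejected in 4.3% to 6.7% across all settings, which is nominal within simulation error.

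**Step 3: size for a continuous covariate with independent errors.** With reliability R, the correlation of baseline and 6-month score is R, and Z correlates 0.5√R with each. The partial correlation of Z with the 6-month score is

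0.5√R(1 − R) / √[(1 − 0.25R)(1 − R²)].

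At R = 0.7 this is 0.1255 / √(0.825 × 0.51) = 0.1935, so partial eta squared is 0.037. At R = 0.6 and 0.8 it is 0.044 and 0.028. False rejection is about 30%, 26% and 20% at R = 0.6, 0.7 and 0.8, against about 5% for raw change. The rate depends on the assumed link to baseline. With a correlation of 0.3 with the observed baseline score it is 10% to 22%; with 0.5 it is 20% to 47% (r from 0.8 down to 0.5).

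**Step 4: RMBPC with shared error.** By Table 1 (Section 17) the caregiver rates the RMBPC at the same visits as the Zarit, CES-D and GAD-7, so baseline errors may be correlated. Assumed: outcome reliability 0.7, RMBPC reliability 0.8, true correlation 0.5.

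| Error correlation | Baseline-adjusted | Raw change |
|---|---|---|
| 0 | 21% | 5% |
| 0.3 | 10% | 10% |
| 0.5 | 6% | 19% |
| 0.7 | 5% | 33% to 36% |

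The raw-change artefact runs the other way: higher RMBPC looks like more improvement.

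**Step 5: the terms that are safe.** With r = 0.7 and d = 0.8, the mean Group × Z estimate under no effect was −0.002 baseline-adjusted and 0.000 unadjusted, and the adjusted test rejected in 4.8%.

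**The case against.** The baseline-adjusted coefficient is a legitimate quantity: the difference in change among people who start level. Section 6 does not say whether its change-score hypotheses are conditional on baseline, and Section 20 hedges its claim as only essentially an interaction. Aim 3 is exploratory within a pilot. Raw change is not assumption-free either, as Step 4 shows. All of this stands. It limits the fault to the label and to which model tests which hypothesis; it does not make the two quantities equal.

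A reader might infer more than the documents support:

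- **That the pooled effects are simply invalid.** They answer a different question from the one named.
- **That effects appear even if nobody changes.** If every observed change were zero, the coefficient would be zero. The artefact needs measurement error or ordinary fluctuation around unchanged true scores.
- **That the error rate is always several times nominal.** For spousal status it can be close to 5%.
- **That the artefact breaches the plan's .01 bar for partial eta squared.** Section 20 sets that bar for between-group effects. A null covariate exceeds it in about half of samples of 50 anyway (50% to 53%).
- **That raw change should replace the adjusted model throughout.** For RMBPC this could replace a bias against the hypothesis with one in its favor.

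**Conclusion.** The concern holds in limited form. Section 20's Time by Covariate reading is wrong for the model it specifies, and two Aim 3 hypotheses lean on it. That part is algebra and needs no assumption.

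The size does rest on assumptions, because the documents give no correlations. At n = 50, a 5% level and no true change, the false-positive rate runs from about 5% to 6% (0.3 SD gap, r = 0.9) to about 30% (0.8 SD gap, r = 0.5, or a continuous covariate correlated 0.5 with the true outcome at reliability 0.6). A stronger link to baseline would push it higher. Errors shared between RMBPC and the outcomes would lower it for the adjusted model and raise it for raw change.

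The treatment comparison in Aim 2 is untouched. So are the Group by covariate terms, including the expected attenuation of the spousal gap under CC+C, because randomization balances baseline within covariate levels in expectation.

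**What to change.** In Section 20, Data Analysis:

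1. Delete the Time by Covariate parenthetical and describe baseline-adjusted covariate effects as conditional on the baseline score.
2. For the spousal-status hypothesis on change, test the Time by spousal-status term itself: raw change on Group and spousal status, without the baseline outcome score.
3. For RMBPC, report both the raw-change and the baseline-adjusted estimates, and claim an effect on change only if they agree. State the reason: same-visit ratings by the same caregiver can bias raw change in the opposite direction.
4. Keep the baseline-adjusted ANCOVA for Group and for Group by covariate.

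The cost is a short wording change, one extra model per outcome, and a somewhat less precise raw-change estimate. No data collection changes.
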